9. OUTPUT PRESENTATIONS

[Appendix 1](#) shows conventions for presentation of data in outputs.

The templates provided with this SAP describe the presentations for this study and therefore the format and content of the summary tables, figures and listings to be provided by IQVIA Biostatistics.

10. DISPOSITION AND WITHDRAWALS

All patients who provide informed consent will be accounted for in this study.

The frequency and percentage of randomized patients who completed week 18 or discontinued early as well as completed the trial will be summarized for each treatment group. Reason for discontinuation during week 18 will be summarized. The summary of reason for discontinuation from the study will also be presented.

The number and proportion of patients withdrawing the study during the run-in phase will be presented. The number and proportion of patients in each population will also be summarized.

A listing of patients who fail the inclusion/exclusion criteria will be produced.

A summary of major protocol deviations will be provided as frequency and percentages. Protocol deviations in the run-in phase will be summarized separately. A list of all major protocol deviations will also be provided.

11. DEMOGRAPHIC AND OTHER BASELINE CHARACTERISTICS

Demographic data and other baseline characteristics will be presented for the RND and SAF populations.

The continuous demographic/baseline variables will be summarized using the mean, median, standard deviation, minimum, and maximum values. For categorical (nominal) variables, the number and percentage of patients will be used. No statistical testing will be carried out for demographic or other baseline characteristics. All demographic and baseline characteristics will be presented in a listing.

The following demographic and other baseline characteristics will be reported for this study:

- Age (years) - calculated relative to date of informed consent
- Gender
- Race

Document: \sasdata\Mylan\Insulin_glargine\SYA22825\Biostatistics\Documentation\SAP\MYL-1501D-3004_SAP_Final_2_0_clean.doc

Author: [name]

Version Number:

2.0

Version Date:

18OCT2018

Template No: CS_TP_BS016 Revision 4

Reference: CS_WI_BS005

Effective Date: 01Apr2016

Copyright © 2009, 2010, 2012, 2016 Quintiles Transnational Corp. All rights reserved.

The contents of this document are confidential and proprietary to Quintiles Transnational Corp. Unauthorized use, disclosure or reproduction is strictly prohibited.

Analysis Plan Template

- Ethnicity
- Weight (kg)
- Height (cm)
- BMI (kg/m²)
- Duration of diabetes (years)
- Time of glargine administration (morning, evening)
- Baseline fasting plasma glucose (mmol/L)
- Baseline HbA1c (%)
- Insulin use prior to screening (yes, no)
- Fasting C-Peptide, HIV, HBsAg and HCVAb (positive, negative)

11.1. DERIVATIONS

- $BMI (kg/m^2) = weight (kg) / height (m)^2$
- $Duration\ of\ diabetes\ (years) = ((date\ of\ screening - date\ of\ onset\ of\ diabetes) + 1) / 365.25$

12. MEDICAL HISTORY

Medical History information will be presented for the SAF and coded using Medical Dictionary for Regulatory Activities (MedDRA) dictionary version 20. Coded medical history terms will be summarized by System Organ Class (SOC) and Preferred Term (PT), by treatment group. Multiple entries for an individual patient under same SOC/PT will only be counted once.

13. MEDICATIONS

Medications will be presented for the SAF and coded using WHO Drug dictionary 01SEP2017.

See [Appendix 2](#) for handling of partial dates for medications, in the case where it is not possible to define a medication as prior or concomitant, the medication will be classified by the worst case; i.e. concomitant.

- 'Prior' medications are medications which started and stopped prior to the reference start date.

Document: \sasdata\Mylan\Insulin_glargine\SYA22825\Biostatistics\Documentation\SAP\MYL-1501D-3004_SAP_Final_2_0_clean.doc

Author: [name]

Version Number:

2.0

Version Date:

18OCT2018

Template No: CS_TP_BS016 Revision 4
Effective Date: 01Apr2016

Reference: CS_WI_BS005

Analysis Plan Template

- Insulin use prior first dose are any insulin medication used prior to screening visit.
- ‘Concomitant’ medications are medications which:
 - o started prior to, on or after the randomization date
 - o AND ended on or after the randomization date of study medication or were ongoing at the end of the study.

Prior and concomitant medication will be summarized by treatment group. The number of patients taking each medication will be presented by Anatomical Therapeutic Chemical (ATC) names (levels 1, 2, 3). Each patient taking the same therapy more than once will be counted once within each ATC code level. All prior and concomitant medications will be presented in data listing. A separate listing on prohibited medications will also be provided.

14. STUDY MEDICATION EXPOSURE

Exposure to study medication in days will be presented for the SAF.

The exposure will be summarized for each treatment group using the mean, standard deviation, median, minimum and maximum. Interruptions, compliance, and dose changes are not taken into account for duration of exposure.

14.1. DERIVATIONS

Duration of exposure days = date of last study medication administration minus the date of reference day + 1.

Where the reference start date is defined in [section 6.1](#) and the date of last study medication will be taken from the “End of Treatment” form.

15. STUDY TREATMENT NON-COMPLIANCE

Patient will be identified as study treatment non-compliant if the patient meets any following criteria:

- Missing total meal time insulin daily since last visit
- Missing basal insulin daily since last visit
- Took two times more basal insulin daily since last visit
- Took less or more than prescribed basal insulin dose units daily since last visit

Number and proportion of patients with non-compliance will be summarized along with individual categories of non-compliance for each category.

The non compliance proportion is defined as total accumulative non-compliant days/duration of treatment exposure in days. Summary of non-compliance proportion will be performed by each non-

Document: \sasdata\Mylan\Insulin_glargine\SYA22825\Biostatistics\Documentation\SAP\MYL-1501D-3004_SAP_Final_2_0 clean.doc

Author: [name]

Version Number: 2.0

Version Date: 18OCT2018

Template No: CS_TP_BS016 Revision 4
Effective Date: 01Apr2016

Reference: CS_WI_BS005

Analysis Plan Template

compliance category for each treatment group. The treatment groups will be compared by using an ANOVA model which will include treatment and pooled-site.

16. EFFICACY OUTCOMES

16.1. PRIMARY EFFICACY

16.1.1. PRIMARY EFFICACY VARIABLE

The primary efficacy variable is change in HbA1c from baseline to week 18 for the ITT population. The HbA1c is analyzed by central laboratory Q2Solutions.

16.1.2. MISSING DATA METHOD AND DATA OBSERVED UNDER RESCUE MEDICATION FOR PRIMARY EFFICACY VARIABLE

After having mapped data captured at unscheduled and/or early termination visits (if any) to schedule missing visits using visit windows technique (refer to [section 7.4](#)), MI will be used for the primary efficacy analysis. Refer to section 16.1.3 for more details.

If subjects initiate rescue medication after Week 12, HbA1c value at Week 18 or subjects who switch to their own insulin Lantus, will be considered as missing and imputed as described above i.e., first remapped data collected at unscheduled/early termination visits (if any) to Week 18 and then, use MI to impute remaining Week 18 data.

16.1.3. PRIMARY ANALYSIS OF PRIMARY EFFICACY VARIABLE

Descriptive statistics will be tabulated by treatment and by time point of the actual HbA1c value and the changes from baseline.

The primary objective of this study is to test the hypothesis that MYL-1501D product from Process VI is non-inferior to MYL-1501D product from Process V based on change in HbA1c from baseline to week 18.

The primary efficacy analysis will be performed for the ITT analysis set.

Mean changes from baseline in HbA1c will be analyzed based on all observed data of schedule visits as well as data imputed using the unscheduled/early termination data (if collected) or MI methodology for schedule visits at which no value is captured (refer to section 16.1.2).

MI will be performed under the assumption of missing-at-random (MAR) and will be implemented in two steps.

First, partial imputation assuming MAR will be carried out to impute intermittent (non-monotone) missing data based on multivariate joint Gaussian imputation model using the Markov chain Monte

Document: \sasdata\Mylan\Insulin_glargine\SYA22825\Biostatistics\Documentation\SAP\MYL-1501D-3004_SAP_Final_2_0_clean.doc

Author: [name]

Version Number:

2.0

Version Date:

18OCT2018

Template No: CS_TP_BS016 Revision 4
Effective Date: 01Apr2016

Reference: CS_WI_BS005

Analysis Plan Template

Carlo (MCMC) method. A separate model will be used for each treatment group. The imputation model will include the pooled investigator sites and basal insulin dose time (morning vs. evening) as fixed covariate and observed HbA1c values at baseline (visit 6), week 12 (visit 12) and week 18 (visit 14). The MCMC method in the MI procedure in SAS will be used with multiple chains, 200 burn-in iterations, and a non-informative prior. In case of non-convergence or non-estimability issues, a ridge prior and single model will be considered with treatment group added as explanatory variable to model.

Then, the remaining monotone missing data will be imputed using sequential regression multiple imputation, where a separate regression model is estimated for imputation of each variable (i.e., measurement at each visit) one after the other including the observed values and the values just imputed from the previous visit. Each regression model will include explanatory variables for pooled investigational sites, basal insulin dose time (morning vs. evening), treatment group and all previous (baseline (visit 6), week 12 (visit 12) and week 18 (visit 14)) values of HbA1c.

No rounding or range restrictions will be applied.

Imputed data will consist of 100 imputed datasets. The random seed number for the partial imputation with the MCMC method will be 20171220, and the random seed number for the sequential regression MI will be 171016.

Each of the 100 imputed datasets will be analyzed using the following analysis method. Change from baseline in HbA1c to each post-baseline visit will be calculated based on observed and imputed data. Mean changes from baseline in HbA1c values will be analyzed using a mixed model for repeated measures (MMRM) approach. Restricted maximum likelihood (ReML) estimation will be used. The MMRM model will include the changes from baseline in HbA1c values as dependent variables, the baseline HbA1c values as fixed covariate, pooled investigational sites, basal insulin dose time (morning vs evening), treatment group (MYL 1501D Process V and MYL 1501D Process VI), visit (week 12 and week 18), and treatment group by visit interaction as fixed effects, and subjects as random effect. An unstructured covariance structure will be used to model the within-subject error and the Kenward-Roger approximation will be used to estimate the degrees of freedom. If this analysis fails to converge, the following covariance structures will be tested: AR(1), ARH(1), CS, CSH, TOEP, TOEPH. The covariance structure converging to the best fit, as determined by Akaike's information criteria (AIC) will be used as the primary analysis.

Treatment group comparison at week 18 will be based on the least square mean (LS mean) difference between treatment groups (i.e., MYL 1501D Process VI – MYL 1501D Process V) in change from baseline in HbA1c estimated by the model in each imputed datasets. Results from analysis of each imputed dataset i.e., LS mean differences and their standard error (SE), will be combined using the Rubin's imputation rules to produced pooled LS mean estimate of treatment difference and its 2-sided 95% confidence interval (CI).

Non-inferiority will be established if the upper limit of the two sided 95%CI for the difference (MYL-1501D Process VI minus Process V) of mean change from baseline to endpoint for HbA1c is not greater than 0.4% at week 18.

Refer to [APPENDIX 3](#) for SAS code example.

For graphical display at scheduled visits, the LS Means and 2-sided 95% CI for the changes from baseline in HbA1c to week 12 and week 18 obtained from the MMRM model will be presented by treatment group. Similar graphical display will be presented for the mean actual HbA1c values and SD over time by treatment group.

Document:	\sasdata\Mylan\Insulin_glargine\SYA22825\Biostatistics\Documentation\SAP\MYL-1501D-3004_SAP_Final_2_0_clean.doc		
Author:	[name]	Version Number:	2.0
		Version Date:	18OCT2018
Template No:	CS_TP_BS016 Revision 4	Reference:	CS_WI_BS005
Effective Date:	01Apr2016		

Analysis Plan Template

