7.1 Sample Size Determination

A total of 202 subjects with T1DM are planned to be randomized for this study and will receive either MYL-1501D Process V product or MYL-1501D Process VI product, in a 1:1 ratio.

The sample size estimation is based on assumptions for the change from baseline up to week 18 in HbA1c with either MYL-1501D product from Process V or Process VI. It is assumed, that true mean groups mean difference is 0.03 and standard deviation is equal to 0.74. To demonstrate non-inferiority margin of 0.4% using a 2-sided 95% confidence interval and a 90% power, a total of 172 subjects (86 subjects per treatment group) are required.

To account for a maximum of 15% of subjects being not eligible for the per protocol analysis, a total sample size of 202 is planned to be randomized for this study. The true treatment difference and standard deviation is based on previous study MYL-GAIA-3001.

No replacement of subject will be performed if subject discontinued prematurely from the study.

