7.5. STATISTICAL TESTS

The default significant level will be (5%); confidence intervals will be 95% and all tests will be two-sided, unless otherwise specified in the description of the analyses.

Non-inferiority will be tested at 2.5% (one-sided) level of significance.

Document: \sasdata\Mylan\Insulin_glargine\SYA22825\Biostatistics\Documentation\SAP\MYL-1501D-3004_SAP_Final_2_0_clean.doc

Author: [name]

Version Number:

2.0

Version Date:

18OCT2018

Template No: CS_TP_BS016 Revision 4
Effective Date: 01Apr2016

Reference: CS_WI_BS005

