16.2.3.2. Analysis of change from baseline in fasting plasma glucose

Descriptive statistics will be presented for actual and change from baseline to scheduled visits for fasting plasma glucose. A separate analysis will be done with excluding data with non-fasting status.

Treatment group comparison will be done using the MMRM model as used for the primary endpoint (without imputing missing values), including treatment, visit, treatment-by-visit interaction, pooled-site, basal insulin dosing time, as fixed effects, baseline values as covariate and subjects as random effect.

LSMeans for each treatment group, as well as associated SE and 2-sided 95% CI will be provided by visit. Differences in LSMeans will be calculated and associated 2-sided 95% confidence intervals and p-values will be provided for each visit.

For graphical display at scheduled visits the mean and SD plot will be prepared for the actual plasma

Document: \sasdata\Mylan\Insulin_glargine\SYA22825\Biostatistics\Documentation\SAP\MYL-1501D-3004_SAP_Final_2_0_clean.doc

Author: [name]

Version Number:

2.0

Version Date:

18OCT2018

Template No: CS_TP_BS016 Revision 4

Reference: CS_WI_BS005

Effective Date: 01Apr2016

Analysis Plan Template

glucose measurement by visit and treatment group; LSMeans and 2-sided 95% CI from the same MMRM model will similarly be displayed graphically.

16.2.3.3. Analysis of Change in Daily insulin dose per unit body weight (mealtime, basal insulin and total) for days of 8-point profiles.

Descriptive statistics will be tabulated by treatment and by timepoint. Change from baseline to post-baseline timepoints will also be presented for insulin dose including daily basal insulin dose, daily meal time insulin dose, and daily total insulin dose.

These secondary efficacy parameters will be analyzed using the same MMRM model as the primary efficacy analysis (without imputing missing values). Estimates of the means, LSMeans (2-sided 95% CIs) as well as treatment difference at each visit will be presented.

A graphical display at scheduled visits with the mean and SD plot will be prepared for each of these secondary efficacy endpoints by visit and treatment group; LSMeans and 2-sided 95% CI from the same MMRM model will similarly be displayed graphically.

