proc mixed data = datmichg method = REML order=internal;
  by _imputation_;
  class trtp(ref="Process V") strata sitegr1 avisit usubjid;
  model change = HbA1c_BASE trtp strata avisit sitegr1 trtp*avisit / DDFM =
  KR;
  repeated avisit / type = UN subject = usubjid;
  lsmeans trtp*avisit /diff cl;
  ods output diff = lsdiffs(where=(trt= 'Process IV' and _trt='Process V' and
  visit=_visit));
run;
```

```
/* Combine LSmean Differences for Visit 'Week 12' */
proc mianalyze parms(classvar = full) = lsdiffs (where = (visit = 'Week 12'));
  class trtp*avisit;
  modeleffects trtp*pvisit;
run;
```

```
/* Combine LSmean Differences for Visit 'Week 18' */
proc mianalyze parms(classvar = full) = lsdiffs (where = (visit = 'Week 18'));
  class trtp*avisit;
  modeleffects trtp*avisit;
run;
```

Note to programmers: In case of non-convergence or non-estimability issues for the generation of enough data to produce a monotone missing data pattern, replace the two proc mi by the following:

```
proc mi data = impute3 out = datamono seed =20171220 NIMPUTE=100
  round = 1 1 1 1 1 1 1 1 1 1 1 1 1 1 1 1 1 1 1 1
  min   = 0 0 0 0 0 0 0 0 0 0 0 0 0 0 0 0 0 0 0 0
  max   = 1 1 1 1 1 1 1 1 1 1 1 1 1 1 1 1 1 1 1 1;
  var trtpn  binstime inv01 inv02 inv03 inv04 inv05 inv06 inv07 inv08 inv09
inv10 inv11 inv12 inv13 HbA1c_BASE HbA1c_WK12 HbA1c_WK18;
  mcmc impute = monotone chain= multiple /*prior=ridge=p*/;
run;
```

Document:	\sasdata\Mylan\Insulin_glargine\SYA22825\Biostatistics\Documentation\SAP\MYL-1501D-3004_SAP_Final_2_0 clean.doc		
Author:	[name]	Version Number:	2.0
		Version Date:	18OCT2018
Template No:	CS_TP_BS016 Revision 4	Reference:	CS_WI_BS005
Effective Date:	01Apr2016		

Analysis Plan Template

```
proc mi data = datamono seed = 171016 out = datami NIMPUTE = 1;
  by _imputation_;
  class trtp strata sitegr1;
  var trtp strata sitegr1 HbA1c_BASE HbA1c_WK12 HbA1c_WK18;
  monotone regression;
run;
```

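### The HbA1c MMRM forces one baseline slope on Weeks 12 and 18; adding baseline-by-visit is a near-free precision gain for the Week 18 contrast, not the repair of a bias

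*SAP*

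**What the plan says.** SAP V2.0 section 16.1.3 models change in HbA1c at Weeks 12 and 18 with an unstructured within-subject covariance. The covariates are "the baseline HbA1c values as fixed covariate, pooled investigational sites, basal insulin dose time (morning vs evening"), followed by treatment, visit and treatment-by-visit. No baseline-by-visit term is listed. The Appendix 3 code agrees: "model change = HbA1c_BASE trtp strata avisit sitegr1 trtp*avisit". The Appendix 4 MODEL statement has the same terms, and protocol 7.2.2 names the same effects.

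The imputation step that feeds this model is less restrictive. After a joint Gaussian step for intermittent gaps, monotone missing values are filled by sequential regression, "where a separate regression model is estimated for imputation of each variable (i.e., measurement at each visit) one after the other". Baseline therefore has its own coefficient at each visit.

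The common-slope model is reused in the per-protocol, no-imputation, margin-shift and tipping-point analyses (SAP 16.1.4). It also serves fasting glucose (SAP 16.2.3.2: "baseline values as covariate and subjects as random effect"), insulin dose, SMBG, laboratory values, vital signs, immunogenicity and hypoglycemia rate. The LOCF ANCOVA in 16.1.4 is a single-timepoint model, so it has its own Week 18 slope.

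**The concern.** The Week 18 contrast decides the trial. If the regression of change on baseline differs between Weeks 12 and 18, a single fitted slope is a compromise between the two. Part of the baseline variation then stays in the Week 18 residual, and the interval compared with 0.4% is wider than a visit-specific slope would give. No section of either document argues that the slopes are equal. The imputation step does not assume it, so the analysis model imposes a constraint that the imputed data were not built under. At stake is some precision in the primary interval and in the by-visit intervals of the copied models.

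**Working it through.** **1. The plan's own figure.** Protocol 7.1 sets out "To demonstrate non-inferiority margin of 0.4% using a 2-sided 95% confidence interval and a 90% power" and assumes that the "true mean groups mean difference is 0.03 and standard deviation is equal to 0.74". SAP 7.5 adds: "Non-inferiority will be tested at 2.5% (one-sided) level of significance". The distance from the assumed difference to the margin is 0.4 − 0.03 = 0.37.

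- Normal approximation: n per arm = 2 × (1.960 + 1.282)² × (0.74/0.37)² = 84.1, so 85.
- Noncentral t: 86 per arm gives power 0.903. This reproduces the statement that "a total of 172 subjects (86 subjects per treatment group) are required".
- Inflation: 172/0.85 = 202.4; the plan uses 202.

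The SD of 0.74 is used without covariate adjustment, so the stated sample size does not depend on the baseline term.

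**2. Weight of each visit in the common slope.** Let s12 and s18 be the residual SDs, ρ their correlation, and Δ the difference between the two true slopes. With complete data and unstructured covariance, the generalized least squares common slope gives Week 12 the weight

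w = (s18² − ρ·s12·s18) / (s12² + s18² − 2ρ·s12·s18).

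None of these inputs is in the documents. Assumed: s18 = 0.66, s12 = 0.60 to 0.66, ρ = 0.6 to 0.8.

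- s12 = 0.60, ρ = 0.6: 0.198/0.3204 = 0.62
- s12 = 0.60, ρ = 0.8: 0.1188/0.162 = 0.73
- s12 = 0.66, any ρ: 0.50

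**3. Excess variance at Week 18.** The common slope misses the Week 18 slope by w·Δ. In large samples the variance ratio, common slope over visit-specific slopes, is

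1 + (w·Δ)² × Var(baseline) / s18².

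With an assumed baseline SD of 0.9, Var(baseline)/s18² = 0.81/0.4356 = 1.86.

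| Δ | w = 0.50 | w = 0.73 |
|---|---|---|
| 0 | 0% | 0% |
| 0.1 | 0.5% | 1.0% |
| 0.2 | 1.9% | 4.0% |
| 0.3 | 4.2% | 9.0% |

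A gain of 1 to 4% is worth about 2 to 8 of 202 subjects (0.01 × 202 and 0.04 × 202).

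**4. Simulation.** Two visits, 202 subjects, 14 site pools, the dose-time stratum, 1,500 runs per case; baseline SD 0.9, ρ = 0.8 and a less favourable SD ratio, s12/s18 = 0.85:

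| Δ | SE, common slope | SE, visit-specific |
|---|---|---|
| 0 | 0.0996 | 0.0997 |
| 0.1 | 0.1003 | 0.0997 |
| 0.2 | 0.1023 | 0.0998 |
| 0.3 | 0.1049 | 0.0995 |

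The last row is (0.1049/0.0995)² = 1.11 in variance. The mean Week 18 estimate is nearly identical under the two models (for example 0.0281 and 0.0283 at Δ = 0.3, against a true 0.03), so no bias appears. With equal slopes, a separate simulation under the step 2 and 3 assumptions puts the cost of the extra term at no more than 0.3% of variance.

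**5. Power over a wider grid.** Baseline SD 0.7 to 1.1, Week 18 slope −0.3, s12/s18 of 0.85 to 1.0, ρ 0.6 to 0.8, total SD held at 0.74, 101 per arm. The common slope raises the SE by 0.1 to 1.1% at Δ = 0.1, 0.5 to 4.2% at 0.2 and 1.1 to 9.2% at 0.3. The largest power loss is about 0.2 points at Δ = 0.1 (0.978 to 0.976) and 2.5 points at Δ = 0.3 (0.978 to 0.953). Power stays near 95% or higher throughout.

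**The case against.** The strongest reply is that nothing here is an error. Protocol, SAP text and code agree. The covariance is estimated from the data, so any slope misfit enters the standard error honestly. Nothing in the documents suggests that slopes differ by 0.2 or 0.3 between HbA1c values six weeks apart, and at 0.1 the gain is trivial. All of this stands, and it is why the point is about efficiency only.

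Several stronger readings are tempting, and the documents do not support them:

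- *The Week 18 result is adjusted mainly with the Week 12 slope.* That requires Week 12 to be the less variable visit, which neither document states. With equal SDs the weights are even.
- *The decision interval is certainly too wide.* It is so only if the slopes differ.
- *The mismatch with the imputation model invalidates the analysis.* An imputation model that is more flexible than the analysis model is not a defect. It shows only that equal slopes are not assumed throughout the plan.
- *The trial is underpowered without the term.* The pooling table in SAP 8.2 sums to 219 subjects. With no baseline adjustment at all, that gives about 96% power at SD 0.74 and a difference of 0.03.

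It is also fair to say that the LOCF ANCOVA already uses a Week 18 slope. It is a sensitivity analysis, however, so it leaves the primary model as it is.

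**Conclusion.** The term is absent from the text, the code and the protocol, and one slope is imposed on both visits. Adding it can improve Week 18 precision and costs almost nothing if it proves unnecessary. The table in step 3 gives the size, and it rests wholly on assumed baseline SD, residual SDs, correlation and slope difference. A reader might infer a biased or unsafe non-inferiority conclusion. The documents and the calculations do not support that: the randomized contrast is unbiased with complete or imputed data, and the stated sample size stands. This is a cheap improvement whose benefit depends on unequal slopes and is negligible when they differ by 0.1 or less.

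**What to change.** Before unblinding, add baseline-by-visit (`HbA1c_BASE*avisit`) to the MMRM in SAP 16.1.3 and to the MODEL statements in Appendices 3 and 4. Add the term to protocol 7.2.2 and revise SAP 4.3, which now declares no departures from the protocol; otherwise the two documents would disagree on the primary model. Protocol section 7 requires an amendment for major changes to the primary analysis, so the sponsor should record how it classifies this one. If the term is not added, state why equal slopes are assumed.

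Make the same change, with each variable's own baseline, in the copied MMRMs that have at least two post-baseline visits:

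- HbA1c and fasting lipids (Weeks 12 and 18): 1 degree of freedom
- SMBG and insulin dose (Weeks 6, 12 and 18): 2
- Fasting glucose, vital signs and immunogenicity (Weeks 2, 6, 12 and 18): 3

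Hematology and chemistry need no change, because Week 18 is their only scheduled post-baseline visit. No new data are required. The downside is one to three degrees of freedom per model, plus the edit to the protocol.
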